16.2 Secondary Endpoint Analyses

Population: mITT Analysis Set; PP Analysis Set if less than 90% of mITT.

16.2.1 Progression-free Survival (PFS) on tumor assessment by IRC

PFS time is defined as the time (in months) from randomization to either first observation of disease progression or occurrence of death due to any cause within 84 days of either randomization or the last tumor assessment. The 84-day time window represents the time span between scheduled tumor assessments. The earliest scan date of target/non-target/new lesions will be used as the date of an overall response.

$$\text{PFS (months)} = (\text{date of 1}^{\text{st}} \text{ PD or death} - \text{date of randomization} + 1) / 30.4375.$$

Start date of PFS:

- The date of randomization

Event date is the earliest date of the following events:

- Observed PD before the patient drops out. Overall response of “not evaluable” will be changed to PD if subsequent scan is a PD. PD data from “Overall response” in Assessment of Disease Based on Imaging eCRF will be used.
- PD assessed by imaging after the patient drops out. Imaging PDs collected in the “Survival Follow-Up / Progression Disease” eCRF will be used.

- Death without previously documented PD is observed within 84 days of the date of randomization or last tumor assessment. The Death date is collected on the “Death” eCRF form.

Censoring rules:

- Censored on the date of randomization if no baseline or post-baseline assessment.
- Censored on the date of last tumor assessment or the date of randomization, whatever occurs later, if:
 - Death without previously documented PD is observed not within 84 days of the randomization or last tumor assessment, or
 - Lost to follow-up / withdraw consent without PD/death observed (including also patients whose last available radiological assessment is at least 84 days before data cut-off), or
 - No PD/death observed yet up to the cut-off date (administrative censoring)

An overview of PFS event/censoring rules is given in table 3:

Table 3: PFS Events/censoring rules

	Date of event/censoring	Censored
Events:		
Radiological PD observed before the patient drops out.	Date of PD	No
Radiological PD assessed after the patient drops out.	Date of PD	No
Death without previously documented PD is observed within 84 days of the randomization or the last tumor assessment	Date of death	No
Censoring:		
No baseline or post-baseline assessment	Date of randomization	Yes
Death without previously documented PD is observed not within 84 days of the randomization or the last tumor assessment	Date of last known tumor assessment or date of randomization, whatever occurs later	Yes
Lost to follow-up / withdraw consent without PD/death observed (includes also patients with a radiological assessment that is at least 84 days before data cut-off)	Date of last known tumor assessment or date of randomization, whatever occurs later	Yes
No PD/death observed up to the cut-off date (administrative censoring)	Date of last known tumor assessment or date of randomization, whatever occurs later	Yes

Analysis methods analogous to the ones of the primary endpoint will be employed. Subgroup analyses will be performed for each of the subgroup variables. Kaplan-Meier curves will be presented by treatment arm for each predefined biomarker subgroup.

16.2.2 PFS based on tumor assessment by Investigator

PFS time is defined as the time (in months) from randomization to either first observation of radiologically confirmed PD by the investigator or occurrence of death due to any cause within 84 days of either randomization or the last tumor assessment.

16.2.3 Overall Survival (OS)

A preliminary analysis on OS may be performed when the primary analysis on TTP is analyzed. Final OS analysis will be carried out after the database lock.

Overall survival (OS) time is defined as the time (in months) from randomization to the date of death. For patients who do not have a date of death, the last date known to be alive will be used:

$$\text{OS (months)} = (\text{date of death or last date known to be alive} - \text{the date of randomization} + 1) / 30.4375.$$

Event date:

- Date of death if the death is before the cut-off date

For patients who do not have a date of death, the patient will be censored at the last known alive date, and will be categorized as:

- Administrative censoring: For patients whose last date known to be alive is within 90 days of cutoff date.
- Non-administrative censoring: For patients whose last date known to be alive is outside of 90 days before cutoff date.

The last known alive date will be the latest date of alive dates (refers to Table 4)

Table 4: Data source of alive dates

eCRF or Dataset	CRF Items or Variables
Patient Status / Survival Follow-Up	Last known alive date, follow-up date
SDTM.SV	SVSTDTC, SVENDTC
Adverse Events	Start date, end date
Concomitant Medications	Start date, end date
End of Assessment Visit	Completion/discontinuation date
Additional Follow-Up / Progression Disease	Progression date
Anti-Cancer Treatment After Discontinuation	Start date, end date

Analyses analogous to the ones for TTP will be performed, expect that the survival rate will be estimated at 3-month, 6-month and for every 3 months thereafter as applicable. Subgroup analyses

will be performed for each of the subgroup variables. Kaplan-Meier curves will be presented by treatment arm for each predefined biomarker subgroup.

16.2.4 TTP Assessed by Investigator

TTP assessed by investigator is defined as the time (in months) from randomization to the date of the observation of radiological PD assessed by investigator:

$$\text{TTP (months)} = (\text{date of 1}^{\text{st}} \text{ PD} - \text{date of randomization} + 1) / 30.4375.$$

Analysis methods analogous to the ones of TTP assessed by IRC will employed.

16.2.5 Time-to-Symptomatic Progression (TTSP)

Time-to-symptomatic progression (TTSP) is defined as the time (in months) from the date of randomization to the date of deterioration of symptoms assessed by FHSI-8, defined as the total score increase by at least 4 points compared with the baseline value, or deterioration to ECOG PS of 4.

Start date of TTSP:

- The date of randomization

Event date is the date of the earliest deterioration.

Censoring rules:

- Censored on the date of randomization if no baseline or post-baseline assessment.
- Censored at the date of death, if the patient died without deterioration.
- Censored on the date of last FHSI-8 / ECOG assessment or the date of randomization, whatever occurs later, if:
 - Lost to follow-up / withdraw consent without deterioration observed (includes also patients whose last available FHSI-8 / ECOG assessment is at least 42 days before data cut-off), or
 - No deterioration observed up to the cut-off date (administrative censoring)

The FHSI-8 will be scored by the following scoring guideline (version 4):

FACT Hepatobiliary Symptom Index (FHSI-8)
Scoring Guidelines (Version 4)

- Instructions:*
1. Record answers in "item response" column. If missing, mark with an X
 2. Perform reversals as indicated, and sum individual items to obtain a score.
 3. Multiply the sum of the item scores by the number of items in the subscale, then divide by the number of items answered. This produces the symptom index score.
 4. As with all FACIT questionnaires, a high score is good. Therefore, a score of "0" is a severely symptomatic patient and the highest possible score is an asymptomatic patient.

Subscale	Item Code	Reverse item?	Item response	Item Score	
FHSI-8	GP1	4 -	_____	= _____	
	GP2	4 -	_____	= _____	
	GP4	4 -	_____	= _____	
	Score range: 0-32	C2	4 -	_____	= _____
		CNS7	4 -	_____	= _____
		HI7	4 -	_____	= _____
		Hep2	4 -	_____	= _____
		Hep8	4 -	_____	= _____
Sum individual item scores:				_____	
Multiply by 8:				_____	
Divide by number of items answered:				_____ =FHSI-8 score	

Analyses analogous to the ones of TTP will be performed.

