## Appendix E: New York Heart Association (NYHA) Criteria

Class	Description
I	No limitation: Ordinary physical activity does not cause undue fatigue, dyspnea, or palpitation.
II	Slight limitation of physical activity: Such subjects are comfortable at rest. Ordinary physical activity results in fatigue, palpitations, dyspnea, or angina.
III	Marked limitation of physical activity: Although subjects are comfortable at rest, less than ordinary physical activity will lead to symptoms.
IV	Inability to carry on physical activity without discomfort: Symptoms of congestive heart failure are present even at rest. With any physical activity, increased discomfort is experienced.

Source: Criteria Committee, New York Heart Association, Inc. Diseases of the heart and blood vessels. Nomenclature and criteria for diagnosis. 6th ed. Boston, Little, Brown and Co, 1964:114.

## Appendix F: FACT Hepatobiliary Symptom Index 8

The sponsor will provide training for relevant personnel (e.g., key investigators, clinical research associates) in the administration of the questionnaires so that subjects fill in the questionnaires as completely and accurately as possible. It is important that the significance and relevance of the data are explained carefully to participating subjects so that they are motivated to comply with data collection. The measures are self-reported and the subject must complete the questionnaires in private and should not be given help from relatives or clinic staff; help in interpreting the questions is not allowed. All subjects are required to take part in all PRO assessments. If feasible, ePRO software may be used for direct data entry by the subject.

Below is a list of statements that other people with your illness have said are important. **Please circle or mark 1 number per line to indicate your response as it applies to the past 7 days.**

		Not at all	A little bit	Some- what	Quite a bit	Very much
GP1	I have a lack of energy	0	1	2	3	4
GP2	I have nausea	0	1	2	3	4
GP4	I have pain	0	1	2	3	4
C2	I am losing weight	0	1	2	3	4
CNS7	I have pain in my back	0	1	2	3	4
HI7	I feel fatigued	0	1	2	3	4
Hep2	I am bothered by jaundice or yellow color to my skin	0	1	2	3	4
Hep8	I have discomfort or pain in my stomach area	0	1	2	3	4

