16.3.2 Patient Reported Outcome

Population: mITT Analysis Set

Functional assessment of cancer therapy-hepatobiliary (FACT-HP)

The FACT-HP questionnaire will be scored by the FACT-Hep Scoring Guideline (version 4):

FACT-Hep Scoring Guidelines (Version 4) – Page 1

- Instructions:*
1. Record answers in "item response" column. If missing, mark with an X
 2. Perform reversals as indicated, and sum individual items to obtain a score.
 3. Multiply the sum of the item scores by the number of items in the subscale, then divide by the number of items answered. This produces the subscale score.
 4. Add subscale scores to derive total scores (TOI, FACT-G & FACT-Hep).
 5. **The higher the score, the better the QOL.**

Subscale	Item Code	Reverse item?	Item response	Item Score
PHYSICAL WELL-BEING (PWB) Score range: 0-28	GP1	4	-	_____
	GP2	4	-	_____
	GP3	4	-	_____
	GP4	4	-	_____
	GP5	4	-	_____
	GP6	4	-	_____
	GP7	4	-	_____
Sum individual item scores:				_____
Multiply by 7:				_____
Divide by number of items answered:				_____ = PWB subscale score

SOCIAL/FAMILY WELL-BEING (SWB)	GS1	0	+	_____	= _____
	GS2	0	+	_____	= _____
	GS3	0	+	_____	= _____
	GS4	0	+	_____	= _____
	GS5	0	+	_____	= _____
	GS6	0	+	_____	= _____
	GS7	0	+	_____	= _____
Score range: 0-28					
Sum individual item scores:					_____
Multiply by 7:					_____
Divide by number of items answered:					_____ = SWB subscale score
EMOTIONAL WELL-BEING (EWB)	GE1	4	-	_____	= _____
	GE2	0	+	_____	= _____
	GE3	4	-	_____	= _____
	GE4	4	-	_____	= _____
	GE5	4	-	_____	= _____
	GE6	4	-	_____	= _____
Score range: 0-24					
Sum individual item scores:					_____
Multiply by 6:					_____
Divide by number of items answered:					_____ = EWB subscale score
FUNCTIONAL WELL-BEING (FWB)	GF1	0	+	_____	= _____
	GF2	0	+	_____	= _____
	GF3	0	+	_____	= _____
	GF4	0	+	_____	= _____
Score range: 0-28					
	GF5	0	+	_____	= _____
	GF6	0	+	_____	= _____
	GF7	0	+	_____	= _____
Sum individual item scores:					_____
Multiply by 7:					_____
Divide by number of items answered:					_____ = FWB subscale score

Subscale	Item Code	Reverse item?	Item response	Item Score
HEPATOBIILIARY CANCER SUBSCALE (HCS) Score range: 0-72	C1	4 -	_____	= _____
	C2	4 -	_____	= _____
	C3	0 +	_____	= _____
	C4	0 +	_____	= _____
	C5	4 -	_____	= _____
	C6	0 +	_____	= _____

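### The Phase II SAP counts a 4-point rise in FHSI-8 as symptomatic progression, on a score where a rise means fewer symptoms

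*SAP*

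**What the plan says.** Phase II SAP section 16.2.5 measures TTSP from randomization to deterioration of symptoms on FHSI-8, "defined as the total score increase by at least 4 points compared with the baseline value", or to ECOG PS 4. It adds: "Event date is the date of the earliest deterioration".

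The section then fixes the scoring: "The FHSI-8 will be scored by the following scoring guideline (version 4"). The guideline's instruction is: "Perform reversals as indicated, and sum individual items to obtain a score". All eight items are marked for reversal (4 minus the response). The sum is multiplied by 8 and divided by the number of items answered. The table gives "Score range: 0-32", and the guideline states the direction: "As with all FACIT questionnaires, a high score is good". Zero is described as a severely symptomatic patient and the maximum as an asymptomatic one.

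The increase wording also appears in SAP section 6 (secondary endpoints) and in the protocol synopsis, section 9.3.2 and section 9.5.3.3. The protocol gives no scoring rule for FHSI-8. Its Appendix F shows only the patient form: items worded as symptoms, for example "I am bothered by jaundice or yellow color to my skin", answered from 0 (not at all) to 4 (very much). SAP section 16.3.2 uses the same direction for the longer FACT-Hep questionnaire: "The higher the score, the better the QOL".

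**The concern.** A programmer who computes the score the SAP prescribes, and then applies the threshold the SAP prescribes, flags improvement as symptomatic progression and leaves worsening unflagged. The word deterioration in the same section points the other way, so two instructions for one derivation conflict.

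Protocol section 9.3.2 identifies TTSP as the patient-reported endpoint, and section 9.5.3.3 compares the arms by log-rank test at the 10% level. With the rule as written, the test, hazard ratio and Kaplan-Meier curves would describe time to FHSI-8 improvement or ECOG PS 4. An arm that relieved symptoms sooner would appear to progress sooner, so the apparent direction of benefit could invert. In an open-label trial, the direction of a compared endpoint should not be left to be settled at programming.

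**Working it through.** **Inputs.** The event rule, item reversal, proration and score range come from SAP section 16.2.5. The raw response coding (0 to 4, higher is worse) comes from protocol Appendix F.

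**Score formula.** With responses r on n answered items:

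FHSI-8 = 8 × Σ(4 − r) / n

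**Reproducing the SAP's range.** All eight responses 0 (no symptoms): 8 × 32 / 8 = 32. All eight responses 4 (worst): 8 × 0 / 8 = 0. This matches the stated 0 to 32 range and its anchors.

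**Worked example.** Baseline with every item at 1 has eight item scores of 3, so the score is 24.

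| Change from baseline | New score | Difference | Event under the increase rule? | Event under a decrease rule? |
|---|---|---|---|---|
| Four items worsen by one category | 20 | −4 | No | Yes |
| Four items improve by one category | 28 | +4 | Yes | No |
| All items worsen to the maximum | 0 | −24 | No | Yes |

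**Ceiling.** An increase of 4 must end at 32 or below, so it needs a baseline of 28 or below. On complete forms, patients starting at 29, 30, 31 or 32 (raw symptom sum 3, 2, 1 or 0) cannot have an FHSI-8 event. These are the patients with the fewest symptoms at entry.

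**All complete-form pairs.** Scores 0 to 32 give 33 × 33 = 1,089 baseline/post pairs. Pairs that rise by 4 or more number 29 + 28 + … + 1 = 435. By symmetry 435 fall by 4 or more. Under the rule as written, all 435 improving pairs are events and none of the 435 worsening pairs is.

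**Equivalence of the two repairs.** Expanding the formula:

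8 × Σ(4 − r) / n = 32 − 8 × Σr / n

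The reversed score is therefore 32 minus the raw prorated sum for any number of items answered, so a fall of 4 on one is a rise of 4 on the other. This was checked for n = 1 to 8 and every possible item sum. There are 89 attainable prorated scores, giving 89 × 89 = 7,921 pairs, and the two rules disagree in none of them.

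**Search for a reconciling text.** The modification history (SAP section 4) and the visible list of changes from the protocol (SAP section 9) say nothing about TTSP scoring. No visible text says that the change is taken on unreversed responses.

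**The case against.** The strongest counter-argument is that the intent is plain. The endpoint is named symptomatic progression, the section uses deterioration repeatedly, and the other event route is deterioration to ECOG PS 4. A careful programmer would probably infer a decrease, and nothing in the documents shows how TTSP was actually derived. That stands as a statement about intent. It does not rescue the rule: the only numerical threshold and the only scoring method given produce the opposite endpoint, and independent double programming from the same text could reproduce the error.

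The severity can also be contested. The confirmatory component of Phase II is limited to TTP (protocol section 9.5.1), and TTSP is one of several secondary endpoints. The limited reach is accepted, but TTSP is formally compared between arms and the correction costs almost nothing.

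Three narrower points are fair. The 435-of-1,089 count weights all score pairs equally; it shows that the inversion is complete, not how many patients it would affect. Appendix F is a patient form rather than a scoring manual, so the protocol's increase wording is coherent on raw coding, but the documents do not say that a raw sum was intended. Part of SAP section 9 is redacted, so only its visible text can be said to be silent.

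**Conclusion.** The concern holds and should be corrected. SAP section 16.2.5 contradicts itself: the stated threshold applied to the stated score makes FHSI-8 improvement an event and FHSI-8 worsening a non-event. The inversion is total for the FHSI-8 component, and only the ECOG PS 4 component captures worsening as intended.

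The conclusion rests on the SAP's own scoring table and needs no outside assumption. The effect on the trial's TTSP result cannot be sized, because the documents give no FHSI-8 distribution and do not show the derivation used. The IRC-assessed TTP analysis, the sample size and safety monitoring do not use FHSI-8 and are unaffected.

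**What to change.** Choose one direction and state it explicitly in SAP sections 6 and 16.2.5:

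1. **Decrease on the prescribed score.** Define the FHSI-8 event as a decrease of at least 4 points from baseline on the version 4 (reversed, prorated, 0 to 32) score. The protocol synopsis and sections 9.3.2 and 9.5.3.3 should then be aligned. Protocol changes are documented by written amendment (protocol section 11.5), so this is the more expensive route.
2. **Increase on the raw sum.** Keep the increase of at least 4 points, and state that TTSP uses the unreversed, prorated item sum. The protocol wording can then stand.

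The events are identical, so the choice can be made on convenience. The second option is cheaper because it touches only the SAP. Either way, record the clarification in the SAP's modification history and check the direction in any TTSP derivation already programmed. No new data are needed and there is no effect on patients.

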16.2.6 Antitumor Activity Assessed by IRC

Best Overall Response

Best overall response (BOR) is defined as the best result obtained among all tumor assessment visits from baseline until end of treatment or determination of PD, excluding assessments after tumor surgery.

Not Evaluable (NE) is not considered a valid measurement. Overall response of NE will be changed to PD if subsequent scan is a PD. As a consequence, a BOR of NE will only be assigned if NE is the only one treatment assessment (for instance, a patient having assessments of NE and PD will be assigned BOR of PD).

Patients with BOR of non-CR/non-PD (possible only for patients without measurable disease at baseline) are not considered as having achieved objective response, nor clinical benefit.

The following will be provided:

- The number and percentage of patients with a best overall response (BOR) of CR, PR, SD, PD, non-CR/non-PD, and NE will be tabulated.

- The number and percentage of patients will be tabulated over time grouped by the overall response.
- Bar chart with time to response and duration of trial treatment
- The number and percentage of patients will be tabulated by predefined biomarker subgroup and treatment group over time grouped by the best overall response.

Objective Response Rate (ORR) based on tumor assessment by IRC

The objective response rate is defined as complete response (CR) or partial response (PR) as the best overall response (BOR) according to radiological assessments as adjudicated by the IRC from randomization to first occurrence of PD. Responses do not require confirmation according to RECIST v1.1.

The Cochran-Mantel-Haenszel test will be performed for analysis using the randomization strata, i.e., type of Met+. The Cochran-Mantel-Haenszel will test the following two-sided hypothesis:

$$H_0: \Psi = 1$$

$$H_1: \Psi \neq 1$$

where Ψ defines the common odds ratio across all strata.

The common Mantel-Haenszel odds ratio (OR) adjusted by strata and the corresponding 90% CIs using the variance formula for the log of the common odds ratio estimate will be presented. The odds ratio is defined as the odds of showing response with the investigational drug, divided by the odds of showing response with the control treatment, i.e. an odds ratio greater than one corresponds to a benefit of the investigational arm. The homogeneity of the odds ratio across strata will be checked by the Breslow-Day test, The null hypothesis of no association in any of the strata is tested against the alternative, which says that at least in one stratum there is an association between treatment effect and tumor response. Additional to the Mantel-Haenszel estimate, odds ratios per stratum are indicated with the corresponding exact confidence interval. The common odds ratio with no adjustment by strata and its 90% CI will be provided as well.

The ORR rate will be presented for each treatment group including the corresponding 90% Newcombe-Wilson CIs.

The best percent change (%) from baseline for the sum of longest diameters will be displayed in a waterfall plot.

Disease Control Rate (DCR) by IRC

The disease control rate is defined as the proportion of patients having achieved CR, PR, or stable disease (SD) as the BOR according to radiological assessments from randomization until end of trial treatment the first occurrence of PD. In the case of SD, measurements must have met the SD criteria at least once after study entry at a minimum interval of 42 days after randomization.

The DCR rate and its 90% Newcombe-Wilson CI will be calculated.

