
Statistical methods (includes sample size calculation)
	
Statistical analyses of Phase Ib will be carried out in a descriptive manner, whereas Phase II has a confirmatory component when analyzing TTP.
 
Data of Phase Ib will be analyzed after completion of the dose confirmation phase. Primary statistical analyses will be performed using electronic case report form (eCRF) data obtained until a clinical cut-off date in Phase II, which is determined by the date after the required number of events for the primary endpoint has been reported in the primary analysis population, i.e., 40 TTP events for the modified intent-to-treat (mITT) population in Phase II or on 15 August 2017, whichever occurs first. The final statistical analyses for the Phase II study will be performed at approximately 6 months after the last subject is first dosed. Determination of MET status is planned at Molecular Prescreening (Phase Ib retrospectively, Phase II for subject selection); rescoring will be performed as a quality control measure. The mITT population excludes subjects who were randomized but for whom, retrospectively, a c-Met status 1+ or ‘not assessable’ was detected.
 
All data required for the calculation of time-to-event will be taken from eCRF, but randomization strata will be taken as specified in interactive voice/web response service.
 
The DLT population will be used for analysis of Phase Ib. Statistical analyses in Phase Ib will be carried out in a descriptive manner.
 
The mITT population will be primarily used in the analysis of baseline characteristics and efficacy. Analyses on the mITT population will consider subjects’ allocation to treatment groups as randomized.

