### 9.2 Randomization

Randomization will only occur in Phase II. All eligible subjects will be randomized (1:1 basis) to receive MSC2156119J or sorafenib. Randomization will be performed centrally by using an IVRS.

A stratified permuted block randomization procedure will be employed using the following strata:

- BCLC Stage: Stage B versus Stage C

The purpose of stratification is to ensure an even distribution of the 2 treatment arms within the stratum.

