10.2 Definition of Analysis Sets and Subgroups

Screening Analysis Set (SCR)

The screening (SCR) analysis set includes all patients who have signed the main informed consent (i.e., screening failures plus patients enrolled).

Intent-to-treat Analysis Set (ITT)

The intention-to-treat (ITT) analysis set in Phase II part of this trial consists of all subjects who were randomized to study treatment. Subjects will be allocated as randomized.

Modified Intent-to-Treat Analysis Set (mITT)

The modified intention-to-treat (mITT) analysis set will include all patients with MET+ HCC who were randomized to trial treatment. Subjects with IHC c-Met status 1+ or ‘not assessable’ on re-scoring will be excluded from the primary analysis set. The mITT Analysis Set will be used to assess the tumor activity and the efficacy of the compound. Analyses performed on the mITT set will take into account patients’ allocation to treatment groups as randomized.

Per-Protocol Analysis Set (PP)

The per-protocol (PP) analysis set is defined as all mITT patients who meet the following criteria:

- Histologically or cytologically confirmed hepatocellular carcinoma
- Correct treatment allocation according to randomization or dose selection
- Measurable or evaluable disease at baseline
- Dosed for at least 80% of the planned dosing days for at least one cycle, except for patients discontinued due to early death or progression
- Received only permitted medications or procedures according to this protocol
- The absence of any clinical important protocol deviations (see Section 12.2). The exclusion from PP set will be determined in case-by-case scenario, and will be confirmed by a blind data review meeting prior to the database lock.

PP analysis set data will be presented according to as-randomized principle.

If the PP analysis set includes at least 90% of patients in the mITT analysis set, additional efficacy analyses on the PP analysis set will be omitted as the differences in the results based upon these two analysis sets are expected to be negligible.

CCI

Safety Analysis Set (SAF)

[figure not shown]

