The safety (SAF) analysis set includes all patients who have received at least 1 dose of Tepotinib or sorafenib. The SAF analysis set will be used for all summaries of safety data. Analyses performed on the safety analysis set will consider patients as treated. As an example, if a patient was randomized to control arm, but received active treatment throughout the trial rather than control treatment, the patient’s safety data should be reported under active treatment.

An overview of analysis sets and analyses is given in Table 1:

Table 1: Analysis Sets

Analyses	Modified Intent-to-Treat Analysis Set	Per Protocol Analysis Set	Safety Analysis Set
Baseline Assessments	✓		✓
Past, Concomitant and Post Therapies	✓		
Medical History	✓		✓
Compliance and Exposure			✓
Efficacy: Primary	✓	✓	
Efficacy: Secondary	✓	✓	
Safety Analysis			✓

Subgroup of interest

Subgroup analyses will be performed on subgroups as defined below.

For the purpose of including baseline variables into Cox's proportional hazards model the following subgroup variables are to be used. For variables with more than two categories, an indicator variable will be defined for each category except for the first category, which defines the reference always. The following subgroups will be defined:

- Type of MET+ (please refer to Section 13.3.2)
 - moderate [2+] (reference level)
 - strong [3+]
- Gene amplification status
 - mean gene copy number <5 (reference level)
 - mean gene copy number ≥ 5
- Age
 - age < 65 years (reference level)
 - age ≥ 65 years
- Gender
 - male (reference level)

- female
- Geographic region (please refer to Section 13.1)
 - Greater China
 - outside of Greater China (reference level)
- BCLC stage
 - Stage B (reference level)
 - Stage C
- Vascular invasion and/or extrahepatic spread
 - presence
 - absence (reference level)
- The underlying disease or medical condition related to etiology (please refer to Section 13.3.2):
 - HBV
 - Other (reference level)
- Baseline HBV or HCV status
 - Either HBV or HCV positive
 - Both HBV and HCV negative

- AFP elevation at the baseline (please refer to Section 13.3.2)
 - yes
 - no (reference level)
- Prior local-regional therapy:
 - yes
 - no (reference level)
- Baseline tumor HGF group
 - 0 (reference level)
 - Other
- Baseline plasma shedded cMet group
 - above the median
 - below/at the median (reference level)
- Baseline plasma IL-8 group
 - above the median

- below/at the median (reference level)
- Baseline plasma HGF Group

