The primary analysis will test the equality of TTP between treatment arms in the randomized part of Phase II, based on the mITT population, applying a two-sided stratified log-rank test at a significance level of $\alpha = 10\%$, taking into account the strata used for randomization, i.e., baseline BCLC stage. IVRS strata other than the eCRF strata will be used.

The following null-hypothesis is tested by the Cox's proportional hazards model stratified according to strata used for randomization:

$$H_0: \lambda_{\text{experimental}}(t) = \lambda_{\text{control}}(t)$$

$$H_1: \lambda_{\text{experimental}}(t) = \theta \lambda_{\text{control}}(t), \theta \neq 1,$$

where $\lambda(t)$ represents the hazard at time t and θ the unknown constant of proportionality of hazards in the allocated treatment groups in the randomized part. Ties will be handled by replacing the proportional hazards model by the discrete logistic model. With this ties option the Score-test in the Cox's proportional hazards model is identical to the log-rank test:

```
proc phreg data=xxx;
    strata BCLC;
    model TTE*TTE_censor(1) = treatment / ties = discrete rl;
    ods output globaltests=logRank_TTE (where=(test='Score'));
    parameterestimates = HR_TTE ;
run ;
Where:
TTE_censor = 1 if censored, 0 otherwise
Treatment = 1 if in experimental arm, =0 if in control arm
TTE      = Time to event variable, for primary analysis it is TTP by IRC.
```

The hazard ratio θ and 90% CIs of Tepotinib compared to sorafenib will be calculated by Cox's proportional hazards model stratified by baseline BCLC (stage B vs stage C).

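### The Phase II SAP stratifies the IRC response-rate test by type of MET+ and calls it the randomization stratum, but randomization was stratified only by BCLC stage

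*SAP*

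**What the plan says.** Phase II SAP section 16.2.6, under objective response rate by IRC: "The Cochran-Mantel-Haenszel test will be performed for analysis using the randomization strata, i.e., type of Met"+. The same section then specifies a common Mantel-Haenszel odds ratio with a 90% CI, a Breslow-Day test of homogeneity, and odds ratios per stratum with exact intervals. It also asks for an unadjusted odds ratio and for response rates per arm.

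The randomization factor is given elsewhere as follows.

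- Protocol section 9.2 lists one factor: "BCLC Stage: Stage B versus Stage C". SAP section 7 lists the same one.
- SAP section 16.1, for the primary log-rank test: "taking into account the strata used for randomization, i.e., baseline BCLC stage". The SAS code there stratifies by BCLC.
- On the data source, SAP section 16.1 adds "IVRS strata other than the eCRF strata will be used". The statistical methods part of the protocol synopsis agrees: "randomization strata will be taken as specified in interactive voice/web response service".

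Type of MET+ has a different role. SAP section 10.2 lists it among the subgroups ("Type of MET+ (please refer to Section 13.3.2"), with moderate 2+ staining as the reference level and strong 3+ as the other. Subjects scored 1+ or not assessable "on re-scoring will be excluded from the primary analysis set".

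**The concern.** The sentence in section 16.2.6 does not propose MET type as an additional or alternative adjustment. It states that MET type is the randomization stratum, and that is false. The instruction therefore points two ways: to the randomization strata, which means BCLC stage, and to type of MET+, which means 2+ versus 3+ in the SAP's own subgroup list. Both can be programmed, and they give different tables.

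At stake is the adjusted analysis of IRC response rate. The pooled p-value and odds ratio would shift somewhat. The per-stratum odds ratios and the Breslow-Day test would describe different groups of patients altogether. If MET type were used, the report would also misstate the design. In an open-label trial, the choice of stratifier should not be left to be settled after the data are visible.

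**Working it through.** **1. Passages side by side**

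| Place | Randomization stratum named |
|---|---|
| Protocol 9.2 | BCLC stage, B vs C |
| SAP 7 | BCLC stage, B vs C |
| SAP 16.1, text and code | baseline BCLC stage |
| SAP 16.2.6 | type of MET+ |

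Three places agree and one differs. All are readable current text, so redaction or extraction does not explain the difference. The readable part of SAP section 9 (changes from the protocol) lists no change of strata.

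**2. Worked example of the size**

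The plan states no figure for this point, so there is none to reproduce. The documents also give no response rates, B/C split or 2+/3+ split, so the counts below are assumptions: 45 per arm (the SAP expects about 90 randomized), with 7/45 against 2/45 responders.

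In a stratum with arm sizes n1 and n2, N = n1 + n2, m responders in total, and a and c responders in the test and control arms:

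- E = m·n1/N
- V = n1·n2·m·(N−m) / [N²(N−1)]
- chi-square = (Σa − ΣE)² / ΣV, 1 df, no continuity correction
- Mantel-Haenszel OR = Σ[a(n2−c)/N] / Σ[(n1−a)c/N]

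*By BCLC stage* (B 2/9 vs 1/9; C 5/36 vs 1/36):

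- ΣE = 1.500 + 3.000 = 4.500; ΣV = 0.662 + 1.394 = 2.056
- chi-square = 2.500²/2.056 = 3.04, p = 0.081
- OR = (0.889 + 2.431)/(0.389 + 0.431) = 4.05, 90% CI 1.01 to 16.19

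*By MET type*, with 3+ in 12/45 vs 15/45, a typical chance gap (2+ 5/33 vs 1/30; 3+ 2/12 vs 1/15):

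- ΣE = 3.143 + 1.333 = 4.476; ΣV = 1.376 + 0.684 = 2.060
- chi-square = 2.524²/2.060 = 3.09, p = 0.079
- OR = (2.302 + 1.037)/(0.444 + 0.370) = 4.10, 90% CI 1.03 to 16.35

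Placing 0 to 3 of the 7 test-arm responders and 0 to 1 of the 2 control responders in the 3+ group moves the MET-stratified p-value between 0.068 and 0.102. The two analyses are usually close but can fall on opposite sides of 10%.

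**3. Simulation**

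Assumptions:

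- 90 subjects, 1:1, permuted blocks of 4 within BCLC stage; MET 3+ independent of BCLC stage
- response (control/test) 3%/3%, 10%/10%, 5%/10% and 5%/20%
- Stage C share / MET 3+ share of 80%/30%, 90%/20% and 70%/50%
- odds ratios for response of BCLC stage / MET type of 1/1, 0.5/0.67, 0.33/2.0 and 0.33/3.0
- 4 × 3 × 4 = 48 scenarios, 4,000 trials each, two-sided 10%

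Results, CMH by BCLC stage against CMH by MET type:

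- decisions differ in 1.0% to 5.3% of trials, mean 2.7%
- largest gap in rejection rate is 0.253 against 0.238, about 1.5 percentage points
- adjusted odds ratios differ by a median of 3.9% to 11.8%; the 90th percentile of the difference is 15% to 51%

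**The case against.** The strongest reply is that this is a drafting slip. The operative words direct the analyst to the randomization strata, MET type is only a gloss, and sections 7 and 16.1 make the true stratum plain. A programmer who reads the whole SAP has good grounds to use BCLC stage. That is fair and limits the practical risk. It does not make the sentence correct, because the gloss names a definite and usable variable.

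Second, the size rests on assumed inputs, and 90 is the number expected to be randomized. Response is analysed in the mITT set, which could be smaller by an amount the documents do not give. Both points stand, so the percentages show only an order of magnitude. The contradiction needs no figure.

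Third, MET type is not cleanly defined. Protocol section 9.4 has overexpression versus amplification, SAP section 10.2 has 2+ versus 3+, and SAP section 13.3.2, to which the subgroup list refers, gives no levels. This stands, and it is one more reason not to use MET type as the stratifier.

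Fourth, the choice of test may matter more than the choice of stratum. Protocol section 9.5.3.4 plans an unstratified Fisher's exact test for objective response. On 7/45 against 2/45 this gives p = 0.157, compared with 0.081 and 0.079 for the two CMH versions. In this example the change of test alters the decision at 10% and the change of stratum does not. This is a separate matter. The readable part of SAP section 9 does not list the change to CMH, but that section is partly redacted, so the change may be recorded there.

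**Conclusion.** The concern holds. SAP section 16.2.6 names the wrong factor as the randomization stratum, contradicting the protocol and two other sections of the same SAP. This is certain from the text.

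The consequence is small. It reaches the CMH p-value, the Mantel-Haenszel odds ratio with its interval, the Breslow-Day test and the per-stratum odds ratios for IRC response. It does not touch the unadjusted odds ratio, the per-arm rates or the time-to-progression analysis, which is the only one the protocol calls confirmatory. The readable text does not spell out a CMH analysis for disease control or for investigator-assessed response. A CMH test stratified by MET type would still be valid; it would be mislabelled and not the one the design implies. Discordant decisions in a few percent of trials is a fair indication of size under the assumptions listed. The error should be fixed because it is clear and the correction costs almost nothing.

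**What to change.** In Phase II SAP section 16.2.6, replace type of MET+ with BCLC stage (B versus C) as recorded in the IVRS. This brings the section into line with SAP sections 7 and 16.1. Present any response analysis by MET type (2+ versus 3+) as a subgroup analysis. If CMH is kept in place of the protocol's Fisher's exact test, make sure SAP section 9 lists that change.

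The cost is a one-phrase correction in a dated, versioned SAP amendment. It needs no new data or procedures and changes no sample size, event count, power or alpha.
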